#### *Organization and collaboration*

This project emerges from AFS, SI, and will be performed as a joint effort with the Radiotherapy unit at Gjøvik Hospital, SI and the Unit of Urologic Surgery at Hamar Hospital, SI, and with an active collaboration with HUNT survey researchers. The study is organized with a project leader and a multiprofessional scientific project group as explained above. This scientific group works with input from a group of three user representatives.

## User involvement

A group of three user representatives from The Norwegian Prostate Cancer Society was established in December 2019. Meetings have been arranged to discuss study design and focus to ensure that issues of importance to prostate cancer survivors are addressed by the assessments. The user representatives will further participate in all parts of the study conduct, including evaluation of assessment procedures and the information and consent form, and interpretation and dissemination of results to the public, patients and relatives. Furthermore, through their society, the user representatives will provide an important contribution by motivating their members to participate.

## Ethical considerations

Approval for all parts of the project has been granted from the Regional Committee for Medical Research Ethics, Health Region South-East (REK HSØ) (ID 183868 and 266644) and the Data Protection Official for Research, SI. The study is performed according to the rules of the Helsinki-declaration and registered at ClinTrials.gov. Participation does not inflict upon the participants' medical treatment and does not imply any health risks or deviation from good clinical practice. All participants provide written informed consent.

## Amendment

### Changes to the original protocol

*All changes affecting participants in any way (measurements, choice of instruments etc.) were approved by Regional Ethics Committee prior to enrolment of subjects in the research project.*

- Predefined secondary outcome, page 7 [Local late effects (measured with the Expanded Prostate Composite Instrument for Clinical Practice (EPIC-CP) (objective 1)]. Instrument was changed from EPIC-CP to EPIC-26 (1). Approved by the Regional Ethics Committee (REC) March 10, 2021.
- Study IIB: Objective registrations of physical- and sedentary activity performed using the accelerometer Axivity AX3, page 7. The location of the accelerator was changed to subjects' back and right thigh, not hip and back as originally stated. Moreover, the participants would wear the accelerators continuously for seven days, not restricted to waking hours. Approved by the REC, January 19, 2022.
- Study IIB, page 8: test of cognitive function using the Montreal Cognitive Assessment (MoCA) was omitted from the project. Approved by the REC, November 30, 2021.
- Study IIB: the following registrations were added to those described in the protocol: Height, weight, waist circumference and resting heart rate. Approved by the REC, November 30, 2021.

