#### Predefined secondary outcomes are:

- Physical function (PF) (measured by the QLQ-C30) (objective 1).
- Local late effects (measured with the Expanded Prostate Composite Instrument for Clinical Practice (EPIC-CP) (objective 1)
- Activities of daily living (as in HUNT4 70+) (objective 2)
- Objectively measured physical and sedentary activity (accelerometer counts from seven consecutive days), handgrip strength, and one-legged balance (objective 3).

Expanded Prostate Cancer Index Composite for Clinical Practice, EPIC-CP is a 16-item, widely used questionnaire designed for prostate cancer patients, comprising items on urinary, bowel and sexual disturbances. It is currently in routine use in the quality database at USU, Hamar.

Objective registrations of physical- and sedentary activity will be performed using the accelerometer Axivity AX3, which assesses time spent sitting, lying, standing, walking, running etc. Participants will wear two devices on all waking hours for seven days, one attached to their hip and one to their back. The registrations will be transferred to a designated software for analysis.

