**Objective 1. Statistical approach:** To investigate if global QoL (scores 1-100) (primary outcome) is associated to age at the time of treatment, we will estimate a linear regression model, allowing us to assess possibly non-linear association between global QoL and age. Since several factors may influence QoL, we will adjust the analysis for potential confounders in a multiple linear regression model. The confounders to be included are treatment modality (surgery, RT and surgery followed by RT), cancer characteristic (low/intermediate/high risk), clinical relapse (yes/no), androgen therapy (yes/no), time from treatment, social status (living alone/with partner), education (four categories), and comorbidity score. To avoid uncertainties related to any cancer relapse, we will estimate a similar regression model for patients with no biochemical and clinical relapse as sensitivity analysis. **Sample size:** For the multiple linear regression analyses, sample size according to Green's rule of thumb should at least be  $50+8*m$ , where  $m$  is the number of variables in the model. Due to categorical nature of some of the confounders, the number of variables in the model will be 13, requiring at least 154 participants. The size of the enrolled cohort of approximately 840 participants is clearly sufficient to perform the analysis with enough power.

**Objective 2. Statistical approach:** We will compare health status (a four-category primary outcome) between all older prostate cancer survivors and their matched controls by ordinal

---

 Detailed plan for analyses in separate document «statistical analysis plan»

regression model (nominal if proportional odds assumption is violated). The results will be adjusted for potential pre-defined confounder (social status, comorbidity scores, and relapse), and matching variables (age and education) to avoid residual confounding in a multiple regression model. As sensitivity analysis, the same analysis will be performed excluding survivors with clinical cancer relapse. **Sample size:** For regression model with categorical outcome to yield stable estimates, it is required at least 10 cases in the smallest outcome category per variable in the model. As the model includes 8 variables, at least 80 cases in the smallest category is required, which should be unproblematic given the expected number of older survivors (350) and thrice as many controls.

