**Objective 3. Statistical approach:** We will compare SPPB scores (primary outcome) between the older prostate cancer survivors and their matched controls by bivariate linear regression model, and adjust the results for potential pre-defined confounders (social status, comorbidity scores and health status) and matching variables (age and education) to avoid the residual confounding in a multiple linear regression model. **Sample size:** According to Greens's rule of thumb, with 10 variables in the multiple model we will need at least 130 participants to obtain valid estimates. To cover for possible registration failures for some participants, we will include a random sample of 150 from the older participant group and thrice as many matched controls for these analyses.

**Secondary outcomes** will be assessed in the same way as the primary ones for each objective. The same confounders will be included into the multiple models. The type of regression model will be considered based on the nature of each outcome analysed

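### The handgrip model takes over the SPPB covariates and so leaves out height, although height is now measured in Study IIb; adding it would gain some precision and guard against a possible height imbalance with the controls

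*Combined protocol and SAP*

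**What the plan says.** The list of predefined secondary outcomes assigns these to the physical-performance objective: "Objectively measured physical and sedentary activity (accelerometer counts from seven consecutive days), handgrip strength, and one-legged balance (objective 3". Table 1 specifies a digital hand dynamometer and describes no scaling for body size.

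For the primary SPPB comparison, the Objective 3 paragraph under Strategy for analyses and sample size says the analysis will "adjust the results for potential pre-defined confounders (social status, comorbidity scores and health status) and matching variables (age and education". The paragraph on secondary outcomes carries that set over: "The same confounders will be included into the multiple models". What it leaves open is the form of the model: "The type of regression model will be considered based on the nature of each outcome analysed".

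Under Subjects, survivors must live in Innlandet. Controls are men from surveys in Trøndelag, matched on age and education. The surveys are said to include physical examinations, but height is not named.

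The amendment (Changes to the original protocol) adds four measurements to Study IIb: "the following registrations were added to those described in the protocol: Height, weight, waist circumference and resting heart rate". It assigns them no use in the analysis and does not touch the covariate list.

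**The concern.** The covariates were chosen for a balance and mobility score and are then applied to an absolute measure of force. Absolute grip strength can be expected to depend on body size, and neither matching nor adjustment covers it. Two things follow:

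- Variance in grip that height could explain stays in the error term, so the survivor-control difference is estimated less precisely than the data would allow.
- The groups come from different counties. If their mean heights differ, the part of the grip difference due to height would be read as part of the survivor-control difference. Shorter survivors would look weaker than controls for that reason alone; taller survivors would have a real deficit partly hidden.

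Height is a more suitable covariate than weight or waist, because treatment (androgen therapy in particular) may change the latter two, and adjusting for them could remove part of the effect under study. This is a clinical assumption that the documents do not state.

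**Working it through.** **Inputs from the documents.** 150 survivors and three times as many controls (450); 10 model variables; Green's rule, 50 + 8m.

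**Inputs assumed, because the documents give none.** Grip SD 8 kg (7 to 9 kg as a range); partial correlation r of grip with height, given the planned covariates, 0.2 to 0.5; height SD 6.5 cm; mean height difference 0.5, 1 or 2 cm; two-sided alpha 0.05. The calculation treats the groups as two independent samples.

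**1. The plan's own figure.** The plan states that "with 10 variables in the multiple model we will need at least 130 participants to obtain valid estimates". Green's rule gives 50 + 8×10 = 130, which reproduces it. The Objective 1 figure also reproduces: 50 + 8×13 = 154.

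**2. Is height among the 10 variables?** The plan does not itemise them. Taking health status and education as four categories each, as stated for Objectives 2 and 1: group 1 + social status 1 + comorbidity 1 + health status 3 + age 1 + education 3 = 10. On this coding the count is filled without height.

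**3. Precision without height.** SE = 8×√(1/150 + 1/450) = 0.754 kg. The 95% half-width is 1.96×0.754 = 1.48 kg. With SD 7 or 9 kg the SE is 0.660 or 0.849 kg.

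**4. Precision with height.** The SE is multiplied by √(1 − r²). Leaving height out is equivalent to needing 1/(1 − r²) times as many men.

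| r | SE with height (kg) | SE reduction | Equivalent extra men | Power for an assumed 2 kg difference |
|---|---|---|---|---|
| none | 0.754 | – | – | 75.5% |
| 0.2 | 0.739 | 2.0% | 4% | 77.2% |
| 0.3 | 0.720 | 4.6% | 10% | 79.4% |
| 0.4 | 0.691 | 8.3% | 19% | 82.5% |
| 0.5 | 0.653 | 13.4% | 33% | 86.5% |

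The percentage reductions do not depend on the grip SD; the power figures do.

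**5. Shift if mean heights differ.** Shift = r×(8/6.5)×(height difference in cm). In brackets is the chance of a significant result at the 5% level when there is no survivor effect.

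| r | 0.5 cm | 1 cm | 2 cm |
|---|---|---|---|
| 0.2 | 0.12 kg (5.3%) | 0.25 kg (6.2%) | 0.49 kg (10.0%) |
| 0.3 | 0.18 kg (5.7%) | 0.37 kg (7.8%) | 0.74 kg (16.5%) |
| 0.4 | 0.25 kg (6.2%) | 0.49 kg (10.0%) | 0.98 kg (25.7%) |
| 0.5 | 0.31 kg (6.9%) | 0.62 kg (12.9%) | 1.23 kg (37.2%) |

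With no height difference the shift is zero and only the precision loss in step 4 remains.

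**6. Room for one more term.** With height, m = 11 and 50 + 8×11 = 138. The planned 150 survivors alone cover this, although the margin for registration failures falls from 150 − 130 = 20 to 150 − 138 = 12. Counting controls, the model has 600 men.

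**The case against.** The strongest case against runs as follows.

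- **No imbalance is shown.** The documents contain no heights for either county. This stands. A reader might infer that a body-size difference between the two counties' men is being counted as a survivor effect. The documents support only the conditional statement that a difference, if present, would enter the contrast.
- **Every magnitude is assumed.** This also stands. At r = 0.2 the gain is 2% of the SE, and r must be understood as the correlation left after the planned covariates.
- **Adjustment is not closed off.** The section on other assessments allows such data to be used for adjustment, and the amendment adds height to Study IIb. But that wording is general, does not name height, and does not override the specific rule for secondary outcomes. If it did permit height, the choice would still be open when the data are analysed, which is a reason to settle it now.
- **Silence is not a decision.** The amendment is an appended list and the body was not rewritten; it still names the replaced EPIC version and the omitted cognitive test. A footnote also points to a separate detailed analysis plan whose text is not in the combined document as supplied. Both stand. It cannot be said that the sponsor decided against height, or that the detailed plan omits it.
- **A common covariate set is defensible.** It limits analyst discretion. A prespecified exception for one outcome limits it equally well.
- **Control height may not exist.** This stands, and the fix has to be conditional on it.

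**Conclusion.** The point holds as a minor improvement to one secondary outcome. As written, the protocol analyses handgrip strength without height, although height is measured at the Study IIb visit and matching does not cover body size. Under an assumed partial correlation of 0.2 to 0.5, adding height would reduce the standard error by 2.0% to 13.4%. An assumed mean height difference of 1 cm would move the contrast by 0.25 to 0.62 kg, or about 0.3 to 0.8 standard errors, in either direction. These sizes rest on the assumed grip SD, height SD and correlation. Neither the existence nor the direction of a height difference is established, so the documents do not support a claim that the handgrip comparison is biased. The primary SPPB comparison is unaffected.

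**What to change.** 1. Confirm whether height is recorded for the HUNT4 70+ controls and, if so, request it in the same data delivery.
2. If it is available, state in the secondary-outcomes paragraph and in the detailed analysis plan that the handgrip model includes measured height in addition to the SPPB covariates, or that this model is reported as a prespecified sensitivity analysis. If the detailed plan already does this, bring the protocol text into line with it.
3. State that weight and waist circumference are not added on the same argument, because treatment may change them.
4. If control height is not available, say so and report the handgrip result with that limitation.

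The cost is one more covariate, one more variable in the HUNT4 request, and a covariate set for handgrip that differs from the SPPB model. The men tested bear no extra burden, because their height is already being measured.
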